Appendix C (The IRB-approved Protocol)

chemical concentration) causes the association between the primary risk factor and the outcome to change by 10% or more, then the additional variable is identified as a potential effect modifier.

Objective 5: Examine the relationships between consumer products in a residence, environmental concentrations, and exposure to active ingredients found in consumer product chemicals to support development and evaluation of models for predicting exposure to these chemicals

For each residence, a chemical inventory of the products in the home will be performed (based on available databases of chemicals in products), and compared to media measurements (chemical presence/absence and group comparison of concentrations of chemicals in the consumer products versus other measured chemicals not found in consumer products). This information will be used in more complex analyses.

EPA has recently developed new methods for predicting exposure to chemicals in consumer products. These methods are implemented in the Stochastic Human Exposure and Dose-Simulation Model – High Throughput (SHEDS-HT) human exposure model (Isaacs et al., 2014). In order to accommodate high-throughput chemical assessments, SHEDS-Multimedia has been numerically and operationally modified to reduce user burden and increases run speed. The SHEDS-HT model uses a dynamic fugacity-based source-to-concentration module to estimate indoor concentrations by media (air, dust, and surfaces) for chemicals with indirect exposure scenarios, while direct scenarios (exposure during product use) are addressed via appropriate exposure equations. The concentration estimates, relevant exposure factors, exposure predictions, and human activity data are then used by the SHEDS-HT model to rapidly generate population distributions of potential exposures via dermal, non-dietary ingestion, and inhalation pathways. Due to the small sample size of the EPA pilot study add-on, direct comparison of predicted population SHEDS exposures and those measured in the pilot study may not be of use. However, the pilot study will provide a large number of matched product use, indoor media concentration, exposure (e.g., hand wipes), and biomarker measurements that could be used to evaluate individual algorithms or assumptions of the SHEDS-HT model. If the pilot study methods were incorporated into the main Green Housing Study, then direct comparisons between percentiles of predicted exposures and measured metrics could be performed (e.g., for groups with different consumer product use patterns).

SHEDS-HT is a mechanistic model that simulates the use of products in homes, transport of chemicals in these products into environmental media (air, dust, surfaces) in the residence, and human exposure as people contact the contaminated media. The model relies on algorithms that quantify the relationships between product use, media concentrations, and exposures. These relationships have been evaluated using available limited data (mainly for pesticides). The EPA pilot study add-on to the Green Housing Study will produce multimedia measurements for chemicals having properties much different than the chemicals previously used for model evaluation (i.e., pesticides). Examining these relationships in the EPA pilot study add-on to the Green Housing Study can validate the assumptions and results of the SHEDS-HT model for chemicals having a range of properties beyond those previously examined.

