Appendix C (The IRB-approved Protocol)

Secondary objectives:

- 4) Evaluate exposure to chemicals in household cleaning and personal care products as a modifying factor in interpreting the effectiveness of green housing renovations on reducing the incidence of asthma-like symptoms;
- 5) Examine the relationships between consumer products in a residence, environmental concentrations, and exposure to active ingredients found in consumer product chemicals to support development and evaluation of models for predicting exposure to these chemicals;
- 6) Measure biomarkers of consumer product chemicals for young children in conjunction with environmental measurements to evaluate exposure and dose models;
- 7) Assess rapid, low burden, low cost methods for characterizing consumer product use in the residential environment to predict exposure to chemicals;
- 8) Use low burden techniques and survey instruments to collect current information on children's activities, locations, and dietary habits to support exposure models and databases;
- 9) Use settled dust to identify and classify indoor fungal populations and functions overrepresented among fungal biota;
- 10) Evaluate the feasibility of using a simplified mass balance approach to estimate chemical exposure and dose rates incorporating children's toenail clippings, other multimedia measurements, and activity information;
- 11) Examine the feasibility of obtaining extant community-level data and prepare draft approaches for using such data for children's community exposure factor assessment and multiple stressor effects on estimates of health risks.

To accomplish objective 4 we will collect information on the types of household cleaning and personal care products used inside the home as well as information on the duration and frequency of their use. We will examine the association between the primary risk factor (renovation status) and the outcome (symptom incidence) to evaluate possible modifying effects due to chemicals emitted from consumer products, controlling for medication use. We hypothesize that exposure to household cleaning and personal care products will change the relationship between incidence of asthma-like symptoms and renovations to green housing standards.

Objective 5 will support development and evaluation of models for predicting exposure to consumer product chemicals. Measurement and survey results will be analyzed for linkages to the potential for exposure.

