3.2 Study Location

The third study site will be determined by CDC based on site selection criteria detailed in their funding opportunity announcement. In the Green Housing Study third study site, the target sample size is 32 green renovated homes and 32 comparison homes. The target sample size for the EPA pilot study add-on is the same number of families as are recruited to participate in the Green Housing Study. Thus, n=64 younger siblings (only one sibling per household) will be the maximum number that could be enrolled as part of the EPA pilot study add-on. Participants in each family will include the index child and a sibling of the index child living in the same household, as well as the mother/caregiver. The index child is defined as the child recruited to participate in the Green Housing Study who ranges in age from 7-12 years with a doctor diagnosis of asthma. By including both the index child and a sibling, it is an opportunity to collect exposure information for two children living in the same household, allowing us to explore differences in exposure based on lifestage.

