Appendix C (The IRB-approved Protocol)

Objective	Measurements Required	Proposed Analysis Approach

3) Compare multimedia measurements and survey data between pre- and post-renovation time points in green and traditional low-income housing to assess exposure-related changes in the residence and participants due to renovation activities
	
Chemical concentrations in available media (all chemicals, all media); mold information; activity information; all time points of data available for renovated and non-renovated homes; pre- and post-renovation information
	
Descriptive statistics; univariate statistics to compare chemical concentrations and mold at each time point and across renovated and non-renovated homes; correlations amongst chemicals and media; geometric mean and standard deviation for consumer product analytes in personal, residential, and biological samples by pre- and post-renovation time points; t-tests of differences between pre- and post-renovation time points; t-tests between siblings and pre- and post-renovation time points; non-parametric analysis of survey and activity response differences across time points and between renovated/non-renovated housing

4) Evaluate exposure to chemicals in household cleaning and personal care products as a modifying factor in interpreting the effectiveness of green housing renovations on reducing the incidence of asthma-like symptoms
	
Number of asthma-like symptoms reported by each participant; renovation status; total dust loading/air concentrations of measured cleaning product ingredients
	
Multiple regression models to examine the association between the primary risk factor (renovation status) and the outcome (symptom incidence) before and after including possible modifying factors (chemical concentrations). If inclusion of the additional variable causes the association between the primary risk factor and the outcome to change by 10% or more, then the additional variable is a potential effect modifier. Care will also be taken to assess any contributions to the outcomes of interest that are due to changes in medication and exposure-related behaviors rather than renovation.

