Objective 4: Evaluate exposure to chemicals in household cleaning and personal care products as a modifying factor in interpreting the effectiveness of green housing renovations on reducing the incidence of asthma-like symptoms

Using the consumer product inventory obtained through objective 7, specific chemical ingredients will be gleaned from a publicly available household product ingredients database and from measurements reported by Dodson et al. (2012). Human exposure models will combine the usage frequency questionnaire responses with the inventories to predict anticipated residential concentrations. A select set of indicator chemicals will be used to evaluate this extrapolation through statistical analysis of the relationship between consumer products found in the home and measured chemical concentrations (objective 5). Multiple regression models will then be used to examine the association between the primary risk factor (renovation status) and the outcome (symptom incidence). If inclusion of a possible modifying variable (predicted or measured

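### Objective 4's 10% change-in-coefficient rule screens for confounding or mediation and cannot detect effect modification

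*Protocol*

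**What the plan says.** Section 2.2 of the Protocol states secondary objective 4 as an effect-modification question. The renovation-symptom association is to be examined "to evaluate possible modifying effects due to chemicals emitted from consumer products, controlling for medication use", and the hypothesis is that product exposure "will change the relationship between incidence of asthma-like symptoms and renovations to green housing standards".

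The method is in Section 5.0, in two places. Table 8 compares the renovation association "before and after including possible modifying factors (chemical concentrations", and its rule begins "If inclusion of the additional variable causes the association between the primary risk factor and the outcome to change by 10% or more". The Objective 4 text says "Multiple regression models will then be used to examine the association between the primary risk factor (renovation status) and the outcome (symptom incidence", and then that if a predicted or measured concentration causes the association "to change by 10% or more, then the additional variable is identified as a potential effect modifier".

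Neither place states a product term, a stratified estimate or a test of heterogeneity. The parent study's plan (Appendix A, Section B.2, regression models) does include interactions between green status and background variables. It reads them as showing that the effect is larger under some conditions than under others.

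**The concern.** Effect modification means that the renovation effect differs between homes with low and high concentrations of a chemical. Comparing the renovation coefficient with and without the chemical does not look at that. It shows how much of the crude coefficient is explained by the arms having different concentrations.

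The Protocol itself gives reasons to expect such differences. Objective 3 hypothesises that chemical exposures change after renovation and differ between renovated and non-renovated homes, and Appendix A, Section B.1, says renovation could not be randomly assigned. A chemical that renovation lowers and that affects symptoms is a mediator, and this rule would label it a potential modifier. A chemical that truly alters the renovation effect but is balanced between arms would be passed over. A larger sample does not cure this, and the pilot's results are meant to inform later sites.

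**Working it through.** **Inputs.** From the documents: the 10% rule (Section 5.0, Objective 4 and Table 8); Section 3.2, where "the target sample size is 32 green renovated homes and 32 comparison homes", so 64 homes; standardized asthma effects of 0.232 and 0.40 (Appendix A, Table 23), used here as the size of the renovation effect; and 20% loss to follow-up (Appendix A, Section A.12). Assumed, because the documents give no figure: residual SD 1; chemical slope 0 or 0.3 SD; interaction 0 or 0.4 SD per SD of concentration; and renovation shifting the chemical by 0 or −0.5 SD. The plan states no operating characteristic for the rule, so there is no figure to reproduce.

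**Algebra.** Let R be renovation and X the chemical. In least squares,

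b(crude) − b(adjusted) = g × (mean X in renovated − mean X in comparison),

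where g is the pooled within-arm slope of symptoms on X. With equal arms and equal spread, g is about main effect + interaction/2. The interaction enters only through g and is still multiplied by imbalance. If X is balanced, the shift is zero however strong the modification.

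- *Chemical changed by renovation, no interaction:* 0.3 × (−0.5) = −0.15. Against a total effect of −0.40 the shift is 0.15/0.40 = 37.5%; against −0.232 it is 0.15/0.232 = 64.7%. Both are far above 10%.
- *Reversing modifier, main effect 0.3 and interaction −0.6:* g = 0.3 − 0.6/2 = 0, so nothing moves.

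**Large samples.** With n = 100,000 (linear, 60 runs), a true modifier independent of renovation moved the coefficient by a median 0.2–0.8%. The rule fired in 0% of runs and the product term was significant in 100%. The chemical changed by renovation moved it by 37.6% or 64.8%, and the rule fired in 100%. Poisson and logistic checks (n = 400,000) agree:

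- Pure modifier (interaction 0.3): 0.4% and 0.9% change.
- Reversing modifier: 0.0% in both, with interaction z of −229 and −87.
- Chemical changed by renovation, no interaction: 33% in both (Poisson log rate ratio −0.454 to −0.304).

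**At 64 homes** (linear, 4000 runs; renovation effect 0.40 / 0.232 SD):

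| Chemical | 10% rule fires | Product term p < 0.05 |
|---|---|---|
| Irrelevant | 21% / 34% | 5% / 6% |
| Predicts symptoms only (slope 0.3) | 56% / 68% | 5% / 5% |
| Changed by renovation, no interaction | 88% / 92% | 5% / 5% |
| True modifier (0.4), no main effect | 42% / 55% | 33% / 35% |
| True modifier (0.4), main effect 0.3 | 72% / 81% | 34% / 33% |

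The last two rows fire through chance imbalance. With 32 per arm, the SD of the difference in mean X is √(1/32 + 1/32) = 0.25 SD. For a chemical that only predicts symptoms, the 10% line at an effect of 0.40 is a shift of 0.04, which needs an imbalance of 0.04/0.3 = 0.133 SD. That is only 0.133/0.25 = 0.53 standard errors and is exceeded by chance about 59% of the time (56% simulated).

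The denominator is also unstable. The crude renovation coefficient has a standard error of about 0.25, so effects of 0.232 and 0.40 lie only 0.9 and 1.6 standard errors from zero.

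**Product-term reading.** If including the variable is taken to mean adding an uncentred product term (zero lying 3 SD below the mean), the renovation coefficient becomes the effect at zero concentration. The rule then fires in 95–97% of runs for an irrelevant chemical at 64 homes.

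**Power of the product term.** At 64 homes its standard error is about 0.25. An interaction of 0.4 is 1.6 standard errors, or 33–35% power by simulation (25–27% at 50 homes, roughly 64 × 0.8). Only a very large interaction of 0.7 SD per SD reaches about 75%.

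**The case against.** The strongest reply has four parts.

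- **The label is only a screen.** The Protocol says potential modifier and never declares one. That is fair as to wording, but a screen should favour its target. This one fires most often for chemicals that renovation changes, and it fires more often for a purely prognostic chemical than for a modifier with no main effect.
- **Distortion may have been meant.** The background (Section 1.3) speaks of product chemicals masking or distorting renovation effects, and a change-in-estimate screen suits that question. Table 8 also promises attention to changes in medication and behaviour. But Sections 1.3 and 2.2, Table 8 and the Objective 4 text all name modification. If confounding was meant, the label is what needs correcting.
- **The objective is secondary, in a small pilot.** This is true. No primary objective depends on the rule, and a product term will be imprecise with 64 homes. That limits the consequences but does not make the rule valid.
- **The simulation is a simplification.** It uses one linear outcome per home with assumed effects, whereas the study has reported symptom counts, four visits and possibly siblings. The percentages are therefore illustrative. The direction does not depend on them: the algebra is exact for least squares, and the Poisson and logistic checks agree.

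It is also true that the text does not specify the model form. No product term is stated, and reading one in does not rescue the 10% rule.

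**Conclusion.** The concern holds. The rule fixed in Table 8 and in the Objective 4 text measures imbalance in the chemical multiplied by its slope, so it cannot answer the modification hypothesis of Section 2.2. Under the stated assumptions at 64 homes it flags 21–34% of irrelevant chemicals and 88–92% of chemicals changed by renovation without modification. Its hits on true modifiers (42–81%) come from chance imbalance and main effects, and they disappear as the sample grows. The exact rates depend on the assumed effect sizes; the failure to target modification does not. Because the Protocol sets the numeric rule itself, twice, this is not a detail left to a statistical analysis plan. The consequence is confined to secondary objective 4 and to whatever later sites take from it.

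**What to change.** In Table 8 and the Objective 4 text, replace the 10% rule with a renovation × centred log-concentration product term. Report the interaction with its 95% CI and the renovation effect at a low and a high concentration, and state whether modification is judged on the difference or the ratio scale. Use the pre-renovation concentration as the modifier where possible, so that renovation has not already altered it, and say how chemicals measured after renovation are handled. Label the analysis exploratory, since power for a 0.4 SD interaction is only about one third.

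If the 10% comparison is kept, call it a confounding/mediation screen and draw no modification claim from it.

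The cost is two sentences, with the same data and the same regression framework. It also brings Objective 4 into line with the interaction terms already planned in Appendix A.

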Appendix C (The IRB-approved Protocol)

Quantification of relationship between the dust, surface, and air concentrations will be performed for all chemicals. Correlation coefficients will be calculated for multiple measurement days within single residences as well as across residences. Descriptive statistics of ratio of air concentrations to surface or dust concentrations will be calculated and compared to predicted chemical property-dependent ratios implemented in SHEDS-HT. Similar correlations between media (air, surface, dust) concentrations and biomarker concentrations (within- and between-participants by chemical) will be calculated in an attempt to determine a subset of chemicals for which chemical media concentrations are a useful surrogate for chemical exposures.

Objective 6: Measure biomarkers of consumer product chemicals for young children in conjunction with environmental measurements to evaluate exposure and dose models

Biomarkers will be analyzed in blood and urine samples for a complementary suite of chemicals to the target analytes investigated in the environmental samples. Descriptive and univariate statistics will describe measurements for the population, households, and individuals. Correlation and multivariate analyses/models will compare concentrations such as different biomarkers, different biological media, the same biomarker over time, and biomarkers to parents. This will summarize the data and provide the basis for determining which additional statistical analyses will be undertaken.

More complex analyses will be conducted for chemicals that have detections in at least one environmental and one biological media for at least one time point. Priority will be given to compounds that have existing PBPK models so that simple equations and/or default assumptions will not be required, or compounds that are indicated in asthma morbidity to support CDC study goals. As data permit, compounds with a range of persistence (environmental and biological) will be investigated by models.

Biomarker data can enhance exposure assessment through modeling in both a forward (exposure to dose) and reverse (dose to exposure) direction. Exposure and dose models such as NERL's SHEDS-Multimedia model and its variants use a probabilistic approach to predict the distribution of exposure and dose for a specified population. Inputs to the model include measurements (indoor air, house dust (preferential order: vacuum and surface wipe, socks, hand wipes)) and information collected from this study as primary inputs. These models use either a simple internal or a more complex PBPK model to predict the expected distribution of biomarker concentrations. The predicted distribution of concentrations will be compared (mean comparison by z-test, Chi-squared test for variance, ANOVA) with those measured to evaluate the use of such models and model parameters for young children.

Additionally, biomarker measurements will be analyzed in support of other study objectives. We will evaluate differences between case and control homes using ANOVA (objective 1). We will determine associations between a participant's biomarker concentrations before and after renovations using general linear and/or mixed models (objective 2). We will determine correlations between environmental and biomarker concentrations by chemical using Spearman and Pearson correlations (objective 5).

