Appendix C (The IRB-approved Protocol)

2.3 Sample Size Considerations

The sample size for the EPA pilot study add-on is fixed and dependent on CDC's grantee's ability to recruit and retain participants. Using available chemical concentration data for limonene (Sarigiannis et al., 2011), we can estimate the effect sizes we can see given various sample sizes (assumptions: design effect = 2.0, statistical power = 0.8, alpha level = 0.05, correlation = 0.3).

Example: Limonene in air ($\mu\text{g}/\text{m}^3$)

If non-renovated homes have a mean concentration and standard deviation = $15.0 \pm 19.4 \mu\text{g}/\text{m}^3$, with a fixed sample size of $n=35$ participants in each group (renovated and non-renovated homes), we could see a minimum size difference of $11.9 \mu\text{g}/\text{m}^3$.

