Appendix C (The IRB-approved Protocol)

5.0 DATA ANALYSIS PLAN

Our analysis approach will enable us to evaluate the objectives described in Section 2.0. Study participants will be characterized with regard to demographic variables such as age and gender as well as activity-related metrics from questionnaires and electronic devices. Housing and product information will be characterized based on questionnaire responses and technician information collection. Statistical analyses will be completed for target analytes and survey information at each study time point, as well as comparisons between time points and renovated/non-renovated homes. All media will be analyzed and compared between and among each media type. Cross-sectional, longitudinal, and pre/post renovation analyses will be conducted. Data quality (e.g., percent completion or detected, accuracy, precision) will be assessed to help make decisions on more complex statistical analyses that can be conducted with the available data.

Descriptive statistics, univariate analyses, and correlations will be employed to evaluate the pilot study data collected in the third study site. Descriptive statistics will be developed for all variables to be used in data analyses addressing the research objectives. Categorical variables will be summarized by frequencies, while continuous variables will be summarized by mean, standard deviation, median, and range. Environmental and biological measurement variables such as analyte concentrations in dust and urinary biomarker concentrations will be characterized by mean and standard deviation, median, range, appropriate distribution percentile values, and percent of measurements above the detection limit.

For detection limit censored data distributions, appropriate approaches for reducing bias in distributional parameter estimates will be considered (substitution, maximum-likelihood estimation, or beta-substitution, depending on the degree of censoring and sample sizes). Measurement distributions will be assessed for normality using the Shapiro-Wilks or other appropriate normality test. Depending on the distribution, measurement values may be log-transformed to compute geometric means and geometric standard deviations. Other types of transformations and/or non-parametric analysis methods will be considered if necessary.

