Appendix C (The IRB-approved Protocol)

Objective	Measurements Required	Proposed Analysis Approach

5) Examine the relationships between consumer products in a residence, environmental concentrations, and exposure to active ingredients found in consumer product chemicals to support development and evaluation of models for predicting exposure to these chemicals
	
Household consumer product inventories, house dust, surface wipes, air, blood, urine concentrations
	
Quantification of relationships among media (dust, wipes, air) concentrations by chemical (correlations within and between subjects, descriptive statistics of ratio of air concentrations to surface concentrations); correlation between media (air and dust) concentrations and biomarker concentrations (within and between subjects by chemical); comparison of chemicals (individual or by class) in products found in the home with those found in dust and air (presence/absence) based on available databases of chemical ingredients; comparison of chemicals (individual or by class) in product categories reported as used in the home with those found in media (presence/absence, correlation of magnitude with reported use frequencies) based on available databases of chemical ingredients

6) Measure biomarkers of consumer product chemicals for young children in conjunction with environmental measurements to evaluate exposure and dose models
	
House dust, air, duplicate diet, blood, urine concentrations; activity information; survey information
	
Descriptive statistics; correlation analyses; uni- and multi-variate analyses for biomarker measurements; model runs (e.g., SHEDS, PBPK model, PROCEED) for forward/reverse dosimetry; comparison (t-test, correlations) between measurements and model predictions

7) Assess rapid, low burden, low cost methods for characterizing consumer product use in the residential environment to predict exposure to chemicals
	
Photographs of storage locations for household cleaning products and personal care products; barcode scanner inventory of products
	
EPA investigators will identify products in the photographs (blinded to scanner inventory). Image-based inventories will be evaluated against barcode-based inventories to assess collection accuracy (number of products correctly identified in photo divided by number in scanned inventory)

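### Objective 6 compares predicted with measured biomarker distributions by tests that assume independent data, fixes no scale, ignores siblings and repeat visits, and disagrees with Table 8

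*Protocol*

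**What the plan says.** The Objective 6 text in Section 5.0 (Data Analysis Plan) describes exposure and dose models that predict a distribution of biomarker concentrations, and then names the tests: "The predicted distribution of concentrations will be compared (mean comparison by z-test, Chi-squared test for variance, ANOVA) with those measured to evaluate the use". It states no scale, no handling of related children or repeated visits, and no error rate.

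Table 8, in the Objective 6 row, describes the same step as "comparison (t-test, correlations) between measurements and model predictions". It does not mention a z-test or a variance test.

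The opening of Section 5.0 sets general rules for all measurements. A check of normality comes first. The rule on scale is permissive: "Depending on the distribution, measurement values may be log-transformed to compute geometric means and geometric standard deviations". Beyond that, it leaves further transformations and rank-type methods open where they are needed. These rules are not tied to Objective 6, and they say nothing about dependence.

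On the data structure, Sections 3.2 and 3.3 enrol an index child and one sibling per home, with at most 64 siblings. Section 4.1 schedules four visit periods. Table 7 has sibling urine collected on two days per visit.

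**The concern.** Objective 6 asks whether a model reproduces the biomarker distribution seen in young children. The one-sample chi-squared variance test has its nominal size only for normal, independent data. The z-test of means tolerates skew reasonably well but not correlation between values. If either is applied to skewed or clustered values, a rejection may reflect the shape or structure of the data rather than a fault in the model. With two lists of tests in the protocol, an analyst could also choose between them after seeing the data.

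**Working it through.** The protocol gives no error rate or sample size for Objective 6, so there is no stated figure to reproduce. The check asks how often each test rejects a model that is exactly right, at a nominal two-sided 5%.

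**Inputs**
- 64 homes with two children each and four visits (Sections 3.2, 3.3 and 4.1).
- CV: the add-on's only worked concentration is limonene in air, mean 15.0 and SD 19.4 (Section 2.3), so CV = 19.4/15.0 = 1.29. This is not a biomarker. I therefore use CVs of 0.5, 1.0 and 1.29 as assumptions.
- Shares of log-scale variance due to home (h) and child (c): assumed 0.1/0.1, 0.2/0.2 and 0.3/0.1, so that h + c is 0.2 or 0.4.

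**Step 1. Untransformed, independent lognormal values (simulation)**

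| CV | variance test, n=32 | n=64 | n=128 | z-test with predicted SD, n=64 |
|---|---|---|---|---|
| 0.5 | 23% | 25% | 26% | 5% |
| 1.0 | 49% | 53% | 56% | 5% |
| 1.29 | 60% | 63% | 66% | 5% |

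More data makes the variance test worse. The variance of s² is inflated over the normal case by about (κ − 1)/2, where κ = w⁴ + 2w³ + 3w² − 3 and w = 1 + CV². For CV 0.5, w = 1.25, κ = 8.04 and the inflation is 3.52. The large-sample rejection rate is then 2[1 − Φ(1.96/√3.52)] = 30%. The z-test is close to nominal. If the sample SD replaces the predicted SD it rejects 8–12% at CV 1.29 for n from 32 to 128.

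**Step 2. Log scale, independent values.** Both tests return to 5%.

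**Step 3. Log scale, all visits pooled.** This gives 64 × 2 × 4 = 512 values. The variance of the mean is inflated by DE = 1 + 3(h + c) + 4h, and the variance of s² by about VI = 1 + 3(h + c)² + 4h². The rejection rate is 2[1 − Φ(1.96/√DE)], or the same with VI.

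| h / c | DE | z-test, formula | z-test, simulated | VI | variance test, formula | variance test, simulated |
|---|---|---|---|---|---|---|
| 0.1 / 0.1 | 2.0 | 16.6% | 16.3% | 1.16 | 6.9% | 6.9% |
| 0.2 / 0.2 | 3.0 | 25.8% | 25.7% | 1.64 | 12.6% | 12.6% |
| 0.3 / 0.1 | 3.4 | 28.8% | 29.1% | 1.84 | 14.9% | 14.2% |

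**Step 4. Log scale, one value per child.** This gives 128 values in 64 sibling pairs, so DE = 1 + h = 1.1, 1.2 and 1.3. Simulated z-test rates are 6.2%, 7.5% and 8.4%. Variance-test rates are 5.2%, 5.4% and 6.0%.

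**The case against.** The strongest reply is that nobody would run the variance test on raw data. At CV 1.29 and n of 32 or more, a Shapiro-Wilk test flags raw lognormal values in about 99–100% of samples, so the Section 5.0 check would almost always point to the log scale, where the skew problem disappears. That largely stands. A reader might infer that Objective 6 rejects a correct model 63% of the time. The documents do not support this: the figure belongs to the variance test alone, on untransformed data, with a CV borrowed from limonene in air, and it is not an upper bound.

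The protocol also does not say that visits will be pooled. Section 5.0 plans analyses at each time point, add-on blood is taken only at baseline (Section 4.4), and Section 3.3.2 does not expect every home to have a younger sibling. This stands too. With one value per child the inflation is small.

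Three further inferences go too far:
- The Objective 5 remark that "direct comparison of predicted population SHEDS exposures and those measured in the pilot study may not be of use" concerns population exposures. It is followed by other uses of the matched data, so it is not an admission about Objective 6.
- Failing a test does not trigger reverse dosimetry. The protocol makes that tool optional after large discrepancies.
- Low power with nine values says little here, because the Objective 6 text does not confine the comparison to the nine duplicate-diet participants.

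What the reply leaves untouched is dependence, which the Section 5.0 rules do not address, and the conflict with Table 8. The Objective 6 text itself offers mixed models for before-and-after associations, but not for this comparison.

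**Conclusion.** The point holds in a limited form. The protocol names tests that assume independence, one of which also needs normality, and it fixes neither the scale nor the handling of siblings and visits. Table 8 names a different set for the same step.

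The size depends on choices the protocol leaves open:
- Raw scale, 64 values: the variance test rejects a correct model about 25–63% of the time (assumed CV 0.5–1.29).
- Log scale, visits pooled: about 16–29% for the z-test and 7–14% for the variance test (assumed h + c of 0.2–0.4).
- Log scale, one value per child: about 6–8% and 5–6%.

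Objective 6 is secondary and no accept-or-reject decision hangs on these tests, which limits the harm. Adopting the Table 8 list would settle the conflict but not the dependence, since a t-test that ignores the household assumes independence as well.

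**What to change.** In the Objective 6 text and in Table 8, replace the z-test and the chi-squared variance test with one comparison, worded the same in both places. Work on the log scale. For each chemical, report the ratio of predicted to measured geometric mean and the ratio of predicted to measured geometric SD. Take intervals from a bootstrap that resamples whole households, or from a mixed model with household and child effects. State whether visits are pooled or analysed separately.

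A tolerance stated in advance for how close is close enough would help interpretation. It is optional, and its value is for the sponsor to choose.

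The cost is a change of wording, a little more analysis work and wider intervals. No further data are needed.
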